9.6 Data Analyses

Statistical Analyses: Analyses will be conducted using SPSS. Full descriptive data will be produced. Baseline differences between the yoga and control group (demographic variables and depressive severity) will be assessed and controlled for as necessary. Two analyses will be completed: 1) an MITT and 2) a "completer" analysis. Primary analyses will only include data from the IYG and DYG prior to the crossover. We will conduct exploratory analyses including crossover DYG subjects to increase power.

Missing Data: We will test whether missing data occurred randomly across conditions, in which case it will be handled by replacing data with the scale or sub-scale mean. Where this is not feasible, missing data will be imputed through maximum likelihood estimation or multiple imputation. If missing data is not random, advanced statistical analyses taking into account assumptions of various tests will be conducted.

Adherence: number of heated yoga classes attended will be used as a covariate in the efficacy analyses to determine if participants who go to more classes demonstrate greater improvement in depressive symptoms.

Primary Aim I: To recruit and retain adults with depressive symptoms into a controlled trial of hyperthermic yoga, randomizing 40 participants to each the immediate yoga group (IYG) and delayed yoga group (DYG; control group) with seventy-five percent retention in both groups.

Hypothesis 1a: Seventy-five percent of the each group will complete a week-8 assessment.

Hypothesis 1b: Acceptability of hyperthermic yoga will be high on the Acceptability

Interview.

Screening logs will reveal the proportion of eligible screened individuals enrolled in the study. We will track factors that make participants ineligible or unwilling to participate. The goal is 75% retention, with enrollment defined as completing at least one post-baseline assessment visit. Attendance data will be characterized descriptively and compared between treatment arms by chi-squared analysis. Yoga attendance will be examined as a potential covariate in subsequent analyses. Participants who participated in Yoga will be re-contacted at completion of all patient study interventions for accuracy of Yoga attendance. Patient's will be contacted up to three times before they will be labeled as "Lost to Recontact" in the screening logs.

Primary Aim II: To collect the Inventory of Depressive Symptomatology – Clinician Rated (IDS-CR) scores at screening; baseline; and weeks-1, -3, -5 and -8 to evaluate the efficacy of hyperthermic yoga for depressive symptoms.

Hypothesis II: The IYG will have greater decreases in Inventory of Depressive Symptomatology – Clinician Rated (IDS-CR) scores after 8-weeks compared to the DYG.

Response over 8-weeks defined by 50% or greater decrease on IDS-CR total; remission ≤ 11 on IDS-CR total. Continuous variables will be analyzed by generalized mixed effect modeling, which impute missing values based on maximum likelihood estimates of missing parameters, allowing analysis of all MITT participants. A time-by-condition interaction will be analyzed to test the intervention's efficacy. Relevant potential covariates (e.g., attendance) will also be examined.

Primary Aim III: To collect (a) physiological and (b) psychological mediators of hyperthermic yoga in the IYG and DYG group at screening; baseline; weeks-1, -3, -5 and -8 to evaluate treatment response in the IYG compared to the DYG.

Hypothesis IIIa: Salivary cortisol, and inflammatory markers (i.e., Tumor Necrosis Factor [TNF- α], Interleukin-6 [IL-6], and C-Reactive Protein [CRP]) will significantly decrease, following 5- and 8-weeks of hyperthermic yoga in the IYG compared to the DYG.

Hypothesis IIIb: Perceived stress, mindfulness, and rumination will improve by 5- and 8-weeks in the IYG compared to the DYG.

Latent growth curve modeling will assess potential mechanisms of the treatment effect. The slope (change over time) of the mediator variables will be regressed upon the independent variable (condition). The slope of the dependent variable will also be regressed upon the slope of the mediators. This model will permit assessment of the change in mechanisms as it predicts the change in the dependent variables.

Secondary Aim I: To collect measures of quality of life, general health, physical functioning, decreased perceived stress, anxiety, and sleep in the IYG and DYG at screening; baseline; and weeks-1, -3, -5 and -8 to evaluate hyperthermic yoga for secondary outcome measures.

Secondary Hypothesis I: The IYG will have significant improvements in quality of life, general health, physical functioning, perceived stress, anxiety, and sleep compared to the DYG.

These will be analyzed by the same methods as outlined for Primary Aim II (above).

Secondary Aim II (exploratory): To evaluate the long-term effects of the yoga intervention (1-month post intervention), while controlling for continued yoga participation.

Secondary Hypothesis II: Subjects who choose to continue the yoga practice, either in the IYG or DYG, will have increased effects at 1-month post intervention, per the primary and secondary outcome measures compared to the week-8 assessment.

Within-participant treatment effects will be modeled via Generalized linear modeling, assessing depressive symptoms (and other secondary outcomes) at 1-month post-intervention compared to week 8.

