9.2 Sample Size and Randomization

Sample Size and Power Estimation: Although this study will test for statistical significance, the primary aim of this pilot RCT is to estimate the intervention's effect size to conduct a more definitive R01 study, as is outlined in NIH guidelines for developing behavioral interventions³³. The study was powered conservatively based on an 80% (n=64) ITT sample. Effect sizes for the degree of change in IDS-CR (primary outcome) were estimated for the hyperthermic yoga versus the control using Cohen's d (effect size for t-test). A power analysis found that with an ITT sample of 64 (32 per arm), a two-tailed t-test with an alpha level of .05 will yield a statistical power of 79% to detect a large effect size of .70 and 50% to detect a moderate effect size (.50). Thus, if the effect size falls between moderate and large, power would approach 80%, since the evaluable sample should be between 64 and 80. Preliminary data suggested a moderate effect size of .54 for depression³⁴. We predict a more robust effect size of at least .60-.70, as this is a larger sample recruited specifically for depressive symptoms.

Randomization: Our biostatistician will establish the blind and deliver it to the designated Research Coordinator. Randomization will be done by random permuted block design in blocks of 2 and 4. This method assigns subjects to each intervention group with equal probability, while at the same time generating a balanced design. The random permuted block randomization method also protects against bias due to temporal trends (e.g., experience of research staff, or seasonal effect). This randomization design should balance the heterogeneity of the subjects between groups.

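### Adjustment for baseline depression severity waits on an observed difference between arms; fixing it in advance would sharpen the week-8 IDS-CR comparison at no cost

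*Combined protocol and SAP*

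**What the plan says.** On covariates, section 9.6 (Data Analyses, opening paragraph) says "Baseline differences between the yoga and control group (demographic variables and depressive severity) will be assessed and controlled for as necessary". No test, threshold or list follows.

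Under Primary Aim II in the same section, IDS-CR is collected as "scores at screening; baseline; and weeks-1, -3, -5 and -8". The model is described as follows: "Continuous variables will be analyzed by generalized mixed effect modeling, which impute missing values based on maximum likelihood estimates of missing parameters". On the efficacy test, the text reads "A time-by-condition interaction will be analyzed to test" the intervention's efficacy, and then "Relevant potential covariates (e.g., attendance) will also be examined". Baseline IDS-CR is not named as a covariate, and no constraint on baseline means is mentioned. The coding of time and the role of the screening score are also left open.

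Section 9.2 bases power on "a two-tailed t-test with an alpha level of .05" with 32 analysed per arm, and its effect sizes refer to change in IDS-CR. Allocation is 1:1 in permuted blocks, with no stratification by severity stated. Secondary Aim I is to be analysed by the same methods as Primary Aim II.

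**The concern.** In a randomised trial any baseline difference between arms is a chance difference, so looking for one is a poor way to choose covariates. The reason to use baseline severity is that it predicts week-8 severity, and that holds when the arms happen to match. A rule that waits for a visible imbalance will seldom act, and so gives up nearly all of the available precision.

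Precision matters here. Section 9.2 gives 50% power at an effect of .50, and says the main purpose of the pilot is to estimate an effect size for a larger study. The discretionary wording also means that the model behind that estimate is settled after the arms have been compared.

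**Working it through.** **Inputs from the documents (section 9.2).** 32 per arm, from "The study was powered conservatively based on an 80% (n=64) ITT sample"; two-sided alpha .05; effects .50, .60 and .70, taken on the standard deviation of change.

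**Inputs assumed.** The documents give no correlation (rho) between baseline and week-8 IDS-CR, so I use .3, .5 and .7. I also assume equal variances at the two times and complete data.

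**1. The plan's own figures.** A two-sample t-test with 62 degrees of freedom (noncentral t) gives 78.7% at .70 and 50.4% at .50. The plan states 79% and 50%, so these reproduce. At .60 the same test gives 65.6%, or 67.0% by the normal approximation.

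**2. Variance with time as categories.** With free baseline means, the baseline-to-week-8 interaction contrast is the difference in mean change. In units of the score variance:
- change score: 2(1 − rho)
- baseline-adjusted: 1 − rho²
- ratio: (1 − rho²) / [2(1 − rho)] = (1 + rho)/2

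The ratio is .65, .75 or .85, a cut of 35%, 25% or 15%.

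**3. Power with time as categories.** The effective effect is d / √[(1 + rho)/2]. At d = .60 this is .744, .693 or .651. Each range runs from the noncentral t (61 degrees of freedom when adjusted) to the normal approximation, rounded.

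| rho | d = .60 unadjusted | d = .60 adjusted | d = .70 adjusted (noncentral t; 78.7% unadjusted) |
|---|---|---|---|
| .3 | 66–67% | 83–84% | 92.8% |
| .5 | 66–67% | 78–79% | 88.9% |
| .7 | 66–67% | 73–74% | 84.8% |

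**4. Variance with linear time.** Take weeks 0, 1, 3, 5 and 8 and compound symmetry. The sum of the weeks is 17, the sum of their squares is 99, and 17²/5 = 57.8. Constraining the baseline means to be equal cuts the variance of the slope difference by 57.8(1 − rho) / (99 + 107 rho):
- rho .3: 40.46/131.1 = 31%
- rho .5: 28.9/152.5 = 19%
- rho .7: 17.34/173.9 = 10%

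At d = .60, power goes from about 76–78% to about 90–91%, 85–86% or 81–82%. With autoregressive correlation instead, the cuts are about 36%, 25% and 15%.

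**5. What waiting for an imbalance recovers.** As an illustration, suppose adjustment is made only when a baseline test has p < .05. In 40,000 simulated trials per setting this happened in about 5% of trials. At d = .70 and rho .5, power was 79.3% under that rule and 88.3% when always adjusting. The change-score and adjusted tests disagreed on significance in about 13% of trials, so the choice of model can change the result. Type I error under the rule was 3.6% to 4.8% over the settings tried.

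**The case against.** The strongest reply is that baseline IDS-CR is already in the model. A reader might infer from the covariate sentence that baseline severity is ignored unless the arms differ. The documents do not support that. Primary Aim II lists baseline among the IDS-CR time points and tests a time-by-condition interaction, so on the natural reading baseline is always an outcome row. The sentence governs only additional covariate adjustment. This stands, and it is why the comparison above is with a change score and not with an analysis that discards baseline.

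The second reply is that the size of the gain is not the plan's own number. This also stands. Rho is assumed, the plan states neither the coding of time nor free baseline means, and step 4 shows that linear time with compound symmetry raises the unadjusted power and shrinks the gain. The p < .05 rule in step 5 is an illustration, because the plan sets no threshold. Placing the effect on the week-8 standard deviation reverses the ordering by rho: adjusted power at .70 is then 82.3%, 88.9% or 97.1%. Unequal variances matter too. With baseline SD s0 and week-8 SD s1, the change-score variance exceeds the adjusted variance by (s0 − rho·s1)². That is never negative, but it is zero when s0 = rho·s1. Entry requires an IDS-CR score above 23, which may narrow the baseline spread.

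Two further inferences are tempting. One is that the rule inflates type I error. A strict 5% pretest does not, as step 5 shows; the effect of an unspecified discretion cannot be computed from the documents. The other is that the stated power is wrong. It reproduces, and it describes an unadjusted test.

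The attendance example in "Relevant potential covariates (e.g., attendance) will also be examined" concerns a variable measured after randomisation. It is a separate question and lends no weight here.

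**Conclusion.** The point holds as a free improvement and not as a validity fault. The plan makes covariate adjustment for baseline severity depend on an observed difference between randomised arms, states no criterion, and leaves the final model to be settled after the comparison.

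The cost is the gap between a change-type contrast and a baseline-adjusted one: 15% to 35% of the variance with categorical time, and 10% to 31% with linear time and compound symmetry, for rho from .7 down to .3. These figures assume 32 per arm, complete data and equal variances. The direction held in every model checked; the size depends on rho and on features the plan does not state.

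**What to change.** Two edits are needed, both in section 9.6.

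- **Opening paragraph.** Replace the sentence on baseline differences with: *No covariate is selected by testing for baseline differences.*
- **Primary Aim II.** State that the IDS-CR model constrains the baseline (Visit 2) means of the two arms to be equal and takes the week-8 between-arm difference as the efficacy contrast. Equivalently, model the post-baseline scores with baseline IDS-CR and its interaction with time as covariates, and test the week-8 arm difference. Say also how time is coded and how the screening score is used.

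The second edit is essential. With complete balanced data and a random intercept, adding baseline as a time-constant covariate leaves the time-by-condition estimate unchanged. If only post-baseline rows are kept, that interaction tests divergence after week 1, not the week-8 difference.

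Apply the same approach to each secondary outcome that has a baseline value. The cost is SAP wording only: IDS-CR is already collected at Visit 2, so no visit, measure or participant burden is added.

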8. INTERVENTION DISCONTINUATION

If a subject's overall depressive symptoms significantly increase, or if a subject develops suicidal intent, he/she will be evaluated by a study clinician to determine if referral for clinical intervention is needed. This will be determined per study clinician judgment.

- Subjects who demonstrate an increase in the IDS total score of 25% or greater over baseline or whose QIDS-C score is a >16 (indicating severe depression) will be assessed for referral to evidence-based clinical treatment.
- A “yes” on items 4 or 5 on the Columbia-Suicide Severity Rating Scale, a score of 3 on the suicidal ideation question of the QIDS-C, or a score of 3 on the IDS-CR suicide item will prompt assessment, and if necessary, appropriate referral.
- If a subject reports that worsening severity is due to situational factors and there appears to be no acute risk of self harm or other significant worsening, they will be given the option to be reassessed within 72 hours (most likely via phone) to determine the safety of continuation.
- Patients will also be dropped from the study if they are, in the judgment of the study clinician, deemed to be a safety risk, the intervention appears to making their condition worse, or if new information is uncovered re: an untreated condition (e.g., onset of substance abuse or physical condition) that would affect participation or threaten the integrity of the study.

Disconsolation due to Non-Adherence: if a subject does not attend a yoga session for two weeks, he or she will be discontinued from the intervention – though he or she will be asked to come in for a final assessment visit. If a subject misses more than two consecutive assessment visits, he or she will also be discontinued from the intervention, unless there are extenuating circumstances communicated to the study team. Subjects will be allowed to continue if they are only attending one yoga class during any specified week, though this will be controlled for in analyses – their data will still be useful. If subjects are discontinued from the intervention, they will be included in the modified ITT (MITT) analyses (see section 9 below) and invited for a Visit 6 (final exit visit).

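### Section 9.6 makes class attendance a covariate in the efficacy analyses, and nothing keeps this post-randomisation variable, zero by design in the waitlist arm, out of the primary time-by-condition model

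*Combined protocol and SAP*

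**What the plan says.** The combined protocol and SAP deals with attendance in four places.

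- Section 9.6, Adherence, is firm: "number of heated yoga classes attended will be used as a covariate in the efficacy analyses to determine if participants who go to more classes" benefit more. The purpose is to learn whether "participants who go to more classes demonstrate greater improvement in depressive symptoms".
- Section 9.6, Primary Aim I, is softer: "Yoga attendance will be examined as a potential covariate in subsequent analyses".
- Section 9.6, Primary Aim II, names the efficacy test ("A time-by-condition interaction will be analyzed to test the" efficacy of the intervention) and then adds: "Relevant potential covariates (e.g., attendance) will also be examined".
- Section 8 lets participants continue when "only attending one yoga class during any specified week, though this will be controlled for in analyses", without naming the analyses.

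Two further statements set the scope. On the data window, section 9.6 says "Primary analyses will only include data from the IYG and DYG prior to the crossover". For the secondary outcomes under Secondary Aim I it says "These will be analyzed by the same methods as outlined for Primary Aim II (above").

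Section 6.2.2 places the start of yoga after V2 in the IYG and after V7 in the DYG. No section says that the primary model omits attendance, that an attendance-adjusted fit is secondary, or that it is limited to the yoga phase.

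**The concern.** Hypothesis II compares the arms as randomised. Class count is a consequence of randomisation, and in the pre-crossover window it is zero for everyone on the waitlist. It therefore largely repeats the arm indicator, and its remaining variation lies among IYG participants who chose to attend more or less.

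If a term for the effect of attendance on change enters the primary model, the arm coefficient no longer estimates the effect of offering yoga. It estimates the difference between a yoga participant who attends no classes and a waitlist participant. That is not the effect size section 9.2 wants for planning the R01, and it is estimated with far less precision. The same wording reaches the secondary outcomes, and both the MITT and completer analyses. With the form left open, the adjusted or the unadjusted result could be chosen after the data are seen.

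**Working it through.** **Inputs from the plan.** 32 per arm, two-sided alpha 0.05, and 79% power at d = 0.70 and 50% at d = 0.50 (section 9.2). Adherence is 12 of at least 16 classes (section 5.4).

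**Assumptions.** The documents give no mean or SD of class count. I take mean m = 12 and SD s = 4 in the IYG, with 10/5 and 16/3 as the range. The DYG count is 0, inferred from the waitlist design and the pre-crossover window. Effects are in SD units of change, with improvement positive.

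**1. The plan's own figure.** The SE of the arm difference is √(2/32) = 0.25. Noncentrality is 0.70/0.25 = 2.80 with 62 df, giving 78.7% power; at d = 0.50 it is 2.00, giving 50.4%. Both match section 9.2, so the stated power belongs to a comparison without attendance.

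**2. Plain main effect.** With complete data, a time-constant count shifts a participant's level at all visits and leaves the time-by-condition term alone. In simulated mixed models at weeks 0, 1, 3, 5 and 8 (1,000 runs), rejection was 77.5% without the count and 77.4% with it, SE 0.25 in both. This form cannot show whether more classes bring more improvement.

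**3. Attendance adjusting change** (attendance-by-time, or count in a change-score model). The variance of the arm coefficient is multiplied by 1 + m²/(2s²). If benefit does not depend on classes:

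| Mean/SD | Variance factor | SE | Noncentrality (61 df) | Power |
|---|---|---|---|---|
| 12/4 | 1 + 144/32 = 5.5 | 0.25 × 2.35 = 0.59 | 0.70/0.59 = 1.19 | 21.7% |
| 10/5 | 1 + 100/50 = 3.0 | 0.25 × 1.73 = 0.43 | 0.70/0.43 = 1.62 | 35.6% |
| 16/3 | 1 + 256/18 = 15.2 | 0.25 × 3.90 = 0.98 | 0.70/0.98 = 0.72 | 10.9% |

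The mixed-model simulation at 12/4 agrees: SE 0.61, rejection 21.7%.

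**4. What the arm term estimates.** If a share q of the benefit is linear in classes, the arm term tends to 0.70 × (1 − q): 0.70 at q = 0, 0.35 at q = 0.5 (simulated 0.37, power about 10%), and 0 at q = 1 (rejection about 5% to 6%).

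**5. Attendance related to prognosis.** Let r be the correlation, within the IYG, between class count and the change that would have occurred anyway. The slope on count absorbs r/s per class, so the arm term at zero classes is shifted by −r × m/s. With r = 0.3 this is −0.3 × 12/4 = −0.90 SD, against yoga. With no true effect, simulation (4,000 runs) gave a shift of −0.90 and type I error of 32%; the unadjusted test stayed at about 5%. The estimate in step 3 is thus unbiased only if attendance is unrelated to prognosis.

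**The case against.** The best defence is that the Aim II text already names an unadjusted test. It defines efficacy by the time-by-condition interaction, and the next sentence says that covariates will also be examined, most naturally in addition to that test. The power calculation is unadjusted too. No section mentions an attendance-by-time term, a plain covariate does no material harm, and this is a pilot.

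Much of this stands. A reader might infer that the plan commits the primary test to an attendance-adjusted model; the Aim I and Aim II wording does not support that. A reader might also infer that any use of attendance damages Hypothesis II; step 2 shows otherwise. What remains is that the Adherence sentence is unconditional, Aim II is an efficacy analysis, and the sentence's own question needs a term that acts on change. Pilot status does not excuse this, because section 9.2 makes the effect size the main product.

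A third tempting inference is that the completer analysis fares worse because completers all attend most classes. The documents do not support this. Section 9.3 defines completers by assessment visits, section 8 invites those discontinued for non-attendance to Visit 6, and 16 classes is a minimum rather than a cap. Low attenders can therefore be completers. The problem applies in that set, but nothing shows that it is greater there.

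**Conclusion.** The concern holds as a gap in specification that should be fixed. The plan's statements on attendance differ in force, and none protects the primary model. The harm is conditional: absent or immaterial with a supplementary model or a time-constant main effect, and large if the Adherence sentence is followed inside the primary model in a form that answers its question.

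In that form, with 32 per arm and d = 0.70, power falls from 78.7% to about 22% at 12/4 (11% to 36% over the range) even when benefit does not depend on classes. The arm estimate moves towards zero as more of the benefit depends on classes, and reaches about zero only if all of it does. It should not be called unbiased without adding that attendance must be unrelated to prognosis. At an assumed correlation of 0.3 the bias is about 0.9 SD.

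The attendance mean, SD and correlation are assumptions. The direction of the problem does not depend on them; its size does.

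**What to change.** 1. State in section 9.6 that the pre-crossover time-by-condition efficacy models, for primary and secondary outcomes and in both the MITT and completer analyses, contain no attendance covariate.
2. Replace the Adherence sentence with a separate exploratory dose-response analysis of IDS-CR change on classes attended, using yoga-phase data only (IYG weeks 0 to 8; DYG V7 to V11). Label it non-randomised and report a 95% CI. Note that section 6.2.5 calls V11 a 9-week yoga assessment, so the two windows may not be the same length.
3. Reconcile the analysis wording on attendance in section 8 and under Aims I and II in section 9.6 with this rule.

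The cost is wording only. Sample size, visits and the stated 79% power are unchanged, because section 9.2 already assumes no attendance adjustment. The drawback is that the dose-response estimate will be imprecise. Under fully proportional benefit (0.70/12 = 0.058 SD per class, SD 4 classes), power is about 24% in the IYG alone (n = 32) and at most about 45% if all 64 contribute yoga-phase data. The 95% CI half-width per 4 classes is about 0.37 and 0.25 SD respectively. The result should be read as descriptive.
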